1. INTRODUCTION

This is a Phase 3, global, double-blind, randomized, placebo-controlled study of adjunctive Ganaxolone (GNX) treatment in children and adults with TSC-related epilepsy. The study consists of a 4-week prospective baseline phase, defined as the first 28 days following screening, followed by a double-blind phase consisting of a 4-week titration period and a 12-week maintenance period.

Following completion of the treatment period, participants who are compliant with study conduct will have the option to enroll and be treated with GNX in a separate OLE study, 1042-TSC-3002. All participants entering the OLE will have their dose of study medication adjusted in a double-blind cross-titration over 4 weeks such that all are receiving GNX at study completion. Participants who do not continue in the OLE will undergo a 2- to 4-week double-blind down-titration and taper if discontinuing IP.

Sections 2 and 5 of the Protocol provides a detailed description of the investigational product, target patient population, and potential risks and benefits of treatment with GNX. The purpose of this Statistical Analysis Plan (SAP) is to define the methodology for analyzing and summarizing the data collected during the conduct of Study 1042-TSC-3001.

2. STUDY INFORMATION, OBJECTIVES, AND ENDPOINTS

2.1. Protocol and Case Report Form Version

This SAP is based on 1042-TSC-3001 Protocol Amendment 3 v4.0 dated 12SEP2023, Protocol Addendum (Amd 2) dated 18AUG2023, and case report forms (CRFs) approved 20APR2023. Unless superseded by an amendment, this SAP will be effective for all subsequent Protocol amendments and CRF versions.

2.2. Study Objectives

2.2.1. Primary Objective

The primary objective of the study is: to assess the safety and efficacy of GNX compared to placebo (PBO) as adjunctive therapy for seizures associated with TSC in children and adults as assessed by the change from baseline in the frequency of countable major motor and focal seizures (primary endpoint seizures) during the double-blind phase.

2.2.2. Secondary Objectives

The secondary objectives of the study are to evaluate the efficacy of GNX vs. PBO:

- To determine the percentage of change from baseline in 28-day primary endpoint seizure frequency during the maintenance period.
- To assess the change in focal seizure frequency from baseline during the double-blind phase.
- To assess changes in mood, behavior, and quality of life using the following:
 - ADAMS
 - Peds-QL-FIM
 - SF-36
 - ELDQOL
- To assess overall clinical outcome using the CGI-I scores by the clinician and the parent/caregiver.
- To evaluate the changes in seizure intensity and duration using the CGI CSID.

2.2.4 Safety Objectives

To assess the safety and tolerability of GNX compared with placebo as adjunctive therapy for seizures associated with TSC.

2.3. Study Endpoints

2.3.1. Primary Endpoint

The primary efficacy endpoint is the percentage change from baseline in 28-day primary endpoint seizure frequency during the double-blind phase.

2.3.2. Key Secondary Efficacy Endpoints

- Percentage change from baseline in 28-day primary endpoint seizure frequency during the maintenance period.
- Number (%) of participants considered treatment responders during the double-blind phase.
- Number (%) of participants considered treatment responders during the maintenance period.
- CGI-I at the last scheduled visit in the double-blind phase.

2.3.3. Secondary Efficacy Endpoints (Behavior/Neuropsychiatric/Quality of life):

- Change from baseline in ADAMS total score and sub-score.
- Change from baseline in quality-of-life scales: Peds-QL-FIM, SF-36, and ELDQOL.

2.3.4. Secondary Efficacy Endpoints (Seizure Control):

- Change from baseline in the percentage of seizure-free days during the double-blind phase, based on primary endpoint seizure type.
- Change from baseline in the percentage of seizure-free days during the maintenance phase, based on primary endpoint seizure type.
- CGI-CSID at the last scheduled visit in the double-blind phase.
- Participants with a $\geq 25\%$ and $\geq 75\%$ reduction from baseline in primary endpoint seizure frequency during the double-blind phase.

- Participants with a $\geq 25\%$, $\geq 50\%$, and $\geq 75\%$ reduction from baseline in primary endpoint seizure frequency during the maintenance period.
- Responder analysis for primary endpoint seizures and all seizures during the double-blind phase using the following response categories: $\leq 0\%$, $\geq 0\%$ to < 25%, $\geq 25\%$ to < 50%, $\geq 50\%$ to < 75%, and $\geq 75\%$ to 100%.
- Percent change in 28-day frequency of all seizures.
- Change from baseline in the percentage of seizure-free days, based on all seizure types.
- Change from baseline in the longest seizure-free interval, based on primary endpoint seizure types and all seizure types.

2.3.5. Exploratory Endpoints

Except for the endpoints of seizure frequency during the titration and maintenance periods of the study,

2.3.6. Safety Endpoints

- Incidence and severity of AEs, SAEs, and withdrawals and dose-reductions due to AEs
- Other measures of safety including physical/neurological/developmental examinations, vital sign measurements (eg, blood pressure, heart rate, respiratory rate, and body temperature), 12-lead ECGs, clinical laboratory tests, and suicidal ideation and behavior risk monitoring.

3. STUDY DESIGN

3.1. Randomization

Subjects will be randomized to receive either GNX or PBO in a 1:1 ratio and randomization will be stratified based on current use of Epidiolex. Block randomization will be used with a block size specified in Rave RTSM (randomization and trial supply management) study randomization list settings document.

3.2. Sample Size Considerations

The planned sample size for this study is 128 randomized and dosed subjects. These subjects will be allocated into 2 treatment groups, GNX vs. PBO, in a 1:1 ratio. Sixty-four subjects per group provides at least 90% power for the primary endpoint assuming an estimate of the treatment effect (the actual analysis will use a Wilcoxon rank-sum test, which has approximately the same power as the ANOVA) difference that is at least 25% and a common standard deviation of 43% or less.

3.3. Multiplicity

All endpoints will be assessed descriptively, by the treatment to which the participants are randomized, with point estimates and 95% confidence intervals. The primary and secondary endpoints will be assessed in an inferential manner. Multiplicity control will be used for the primary and key secondary endpoints. A gate keeping approach will be used to control the study-wide Type-I error rate. There is a single primary efficacy endpoint, and formal hypothesis testing will be performed for this endpoint first. If the null hypothesis is rejected for the primary efficacy endpoint at the 2-sided 5% alpha level, then statistical hypothesis testing will be performed sequentially on the 4 key secondary endpoints as the order listed in Section 2.3.2. The testing will stop if the testing result is non-statistically significant. All other non-key secondary and exploratory endpoints will use a 2-sided 5% alpha with no adjustment for multiplicity.

4. STATISTICAL METHODOLOGY

4.1. General Methodology

Unless otherwise stated, SAS® software (SAS Institute Inc, Cary, NC; SAS Enterprise Guide 8.3 Version or later) will be used for the generation of all tables, graphs, and statistical analyses. Summary statistics including the number of subjects (n), mean, standard deviation, median, minimum and maximum will be presented for continuous variables. Generally, the minimum and maximum values will be presented to the same decimal precision as the raw values, the mean and median values to one more, and the standard deviation, to two more decimal places than the raw values. For categorical variables, per category, the absolute counts (n) and percentages (%) of subjects with data, and if appropriate, the number of subjects with missing data, will be presented. Percentages will be presented to one decimal place.

For AEs, medical history and concomitant medications reported on a per-subject basis, the denominator for the percentage calculation will be the number of subjects in each treatment group. A subject will be considered at risk if the subject is in the analysis set and in the subgroup of interest.

If a p-value is less than 0.0001 it will be displayed as "< 0.0001". All p-values larger than 0.0001 will be rounded to 4 decimal places.

4.2. Analysis Sets

For the purposes of analysis, the following analysis sets are defined:

- Intent-to-treat (ITT) Set Includes all randomized participants, who dosed and had at least one post-baseline efficacy assessment. Participants will be summarized within the treatment group to which they were randomized. This set will be used for efficacy analyses.
- Per-protocol (PP) Set Includes all participants in the ITT set who received IP for at least 6 weeks, provided at least 5 weeks of post-baseline seizure data, and without major protocol deviations that affect the efficacy endpoints (defined prior to database lock).
- Safety Analysis Set Includes all randomized participants who receive at least 1 dose of the IP. Participants will be summarized within the treatment group for which they received treatment. This set will be used for the safety analyses.

The ITT analysis set is used to analyze endpoints related to the efficacy objectives and the safety analysis set is used to analyze the endpoints and assessments related to safety. The primary analysis will be performed within the ITT population; supportive analyses in the PP population will also be conducted.

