9.2 Analysis Sets

For the purposes of analysis, the following analysis sets are defined:

Participant Analysis Set	Description
Intent-to-treat (ITT) set	All randomized participants. Participants will be summarized within the treatment group to which they were randomized. This population will be used for efficacy analyses.
Modified Intent-to-treat (mITT) set	All randomized participants who receive at least 1 dose of the IP. Participants will be summarized within the treatment group to which they were randomized. This population will be used for sensitivity analysis for efficacy.
Per-protocol (PP) set	All participants in the ITT analysis set participants who received IP for at least 6 weeks, provided at least 5 weeks of post-baseline seizure data, and without major protocol deviations that affect the efficacy endpoints (defined prior to database lock).
Safety analysis set	All randomized participants who receive at least 1 dose of the IP. Participants will be summarized within the treatment group for which they actually received treatment. This population will be used for the safety analyses.

IP = investigational product.

The Intent-to-treat (ITT) analysis set is used to analyze endpoints related to the efficacy objectives and the safety analysis set is used to analyze the endpoints and assessments related to safety. The primary analysis will be performed within the ITT population; a supportive analysis in the per-protocol (PP) and modified intent-to-treat (mITT) population will also be conducted.

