4.3. Statistical Methods for Efficacy Analyses

4.3.1. Estimand Framework for the Primary Endpoint

Population: The target study population comprises children and adults with TSC-related epilepsy who also meet the inclusion and exclusion criteria as specified in the study protocol. The analysis population is the Intent-to-Treat (ITT) Population defined as all randomized participants.

Variable: The variable is the primary efficacy endpoint, the percentage change from baseline in 28-day primary endpoint seizure frequency during the double-blind phase.

Population-Level Summary: The population-level summary will be the difference of the percentage change on primary efficacy endpoint between GNX and PBO groups and its 2-sided 95% confidence interval.

Accounting for Intercurrent Events (ICEs): Intercurrent events and their handling rules are as follows:

- Discontinuations due to lack of efficacy;
- Discontinuations due to expected (per IB) adverse events.

Both ICEs will be addressed by the treatment policy strategy. The use of rescue medication is allowable at any time during the study. A patient may require rescue medication during the trial but continues with the trial post-rescue medication. The efficacy of the trial treatment will be assessed regardless of the need for rescue medication. Alternative approaches to handling ICEs will be addressed in sensitivity analyses, see Section 4.3.3.

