4.3.2. Primary Efficacy Endpoint

Hypothesis testing will be performed for the primary endpoint: the percentage change in 28-day primary endpoint seizure frequency during the DB phase relative to the baseline, based on the primary endpoint seizure types. The hypothesis testing is:

$$H_0$$
: $\theta_{PBO} = \theta_{GNX}$ H_a : $\theta_{PBO} \neq \theta_{GNX}$

where θ_{GNX} is the percentage change of seizure frequency during the DB phase relative to the baseline for participants who treated with GNX and θ_{PBO} is similarly defined for participants receiving placebo.

Primary endpoint seizure types are defined as the following: focal motor seizures without impairment of consciousness or awareness, focal seizures with impairment of consciousness or awareness with motor features, focal seizures evolving to bilateral, tonic-clonic seizures, and generalized motor seizures including tonic-clonic, bilateral tonic, bilateral clonic, or atonic/drop seizures. Seizures that do not count toward the primary endpoint include: focal aware seizures without motor features (eg, focal nonmotor seizures with or without impaired awareness, absence or myoclonic seizures), infantile or epileptic spasms, and myoclonic seizures.

Post-baseline 28-day seizure frequency will be calculated as the total number of seizures in the double-blind phase divided by the number of days with seizure data in the same period, multiplied by 28. Baseline 28-day seizure frequency will be calculated as the total number of seizures in the baseline phase divided by the number of days with seizure data in the same period, multiplied by 28. The calculation for percent change from baseline in 28-day seizure frequency will be done as follows for each participant:

The baseline, post-baseline, and arithmetic and percent changes from baseline in 28-day seizure frequency will be summarized using descriptive statistics.

The difference between the treatment groups in the percent changes will be tested for statistical significance. The estimate of the median difference and corresponding 95% confidence interval based on the Hodges–Lehmann approach will be provided. Since the percent differences are anticipated to display skewness and/or outliers, the test will be performed using the Wilcoxon Rank-Sum statistic using a 2-sided significance level of 0.05.

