4.3.3. Sensitivity Analysis

Five sensitivity analyses of the primary efficacy endpoint of change in 28-day frequency of the primary seizure types will be performed:

1. Intermittent (random/sporadic) missing data during the DB phase and any missing data during the baseline phase will be assumed missing completely at random and the collected data will be used to calculate the 28-day seizure frequencies. For early drug termination prior to the end of the DB phase, caregivers will be instructed to continue to provide daily seizure records until the end of the 16-week DB phase (hence further preventing missingness).

In the first sensitivity analysis, the following imputation approach will be used for the primary outcome measure when a subject stops recording measurements permanently prior to the end of the DB phase: for those missing days, the corresponding median PBO data will be imputed (irrespective of treatment arm) as follows:

- Partition the subjects in the PBO arm into quartiles, where the quartile equals Floor [Rank*4/(n+1)], where Floor [.] is the integer floor function, Rank is the rank of the 28- day seizure frequency in the PBO arm based on all available PBO measurements during the 4-week baseline phase (tied scores receive tied ranks), and n is the number of subjects in the PBO arm.
- Assign each subject for whom imputation is needed into the quartile that covers the 28-day seizure frequency based on that subject's available measurements during the 4-week baseline phase. If a frequency is lower than the lower bound of the lowest quartile (which could happen only in the GNX arm), then assign that subject to the lowest frequency quartile; likewise, if a frequency is higher than the upper bound of the highest quartile, then assign that subject to the highest frequency quartile. If a frequency falls between two quartiles (which, again, could happen only in the GNX arm), then based on the distances between the frequency and the upper and lower bounds of the lower and higher quartiles, respectively, assign the subject to the closer quartile (in case of a tie, assign to the lower quartile).
- Within each quartile, compute the median 28-day seizure frequency in the PBO arm based on all available PBO measurements during the DB treatment phase. Label that 'X' and define 'A' to be 'X'/28, (i.e., the daily average on placebo during the DB phase).

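### SAP 4.2 narrows ITT below the all-randomised estimand of SAP 4.3.1, so no efficacy analysis keeps participants who leave before dosing or before any post-baseline efficacy assessment

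*SAP*

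**What the plan says.** **The efficacy set.** SAP 4.2 defines ITT thus: "Includes all randomized participants, who dosed and had at least one post-baseline efficacy assessment". It assigns the primary analysis to this set. Section 8 prints this text beside the protocol's definition and gives no reason for the change.

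**The estimand.** SAP 4.3.1 describes the same primary analysis differently: "The analysis population is the Intent-to-Treat (ITT) Population defined as all randomized participants". Protocol 9.2 also makes ITT all randomised.

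**The mITT set.** Protocol 9.2 has a separate mITT set for sensitivity analysis: "All randomized participants who receive at least 1 dose of the IP. Participants will be summarized within the treatment group to which they were randomized". Protocol 9.3.2.1 lists five sensitivity analyses. The fourth uses mITT and the fifth excludes intercurrent events.

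**What the SAP kept.** SAP 4.3.3 opens: "Five sensitivity analyses of the primary efficacy endpoint of change in 28-day frequency of the primary seizure types will be performed". Four numbered items follow, and the last is the exclusion of intercurrent events. No mITT set or mITT analysis appears in the SAP, and section 8 does not mention the removal.

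**Other sets and rules.** The only other efficacy set, per-protocol, is a subset of the SAP 4.2 ITT. The Safety Analysis Set holds everyone dosed, for safety only. SAP 4.1 reports percentages of subjects with data. SAP 4.3.8 does not impute for missing values or early discontinuation.

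**The concern.** The SAP names two populations for one primary analysis. Whoever programs from 4.2 will not estimate what 4.3.1 describes, yet the output will be labelled ITT.

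The exclusion depends on what happens after randomisation: taking the drug, and staying long enough to be assessed. Both can differ by arm. SAP 4.3.1 handles discontinuation for expected adverse events by treatment policy, but a participant who stops for such an event before any assessment would be removed instead. In completed placebo-controlled studies, Protocol 2.2.2.2 reports somnolence in 23.8% on ganaxolone and 7.7% on placebo, so unequal tolerability is plausible.

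Responder status is a key secondary endpoint twice, for the double-blind phase and for the maintenance period. A participant with no diary data can be classed as a non-responder without any count, so nothing forces that person out of the denominator. The SAP has no such rule.

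**Working it through.** **1. How the sets nest.**

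| Set | Randomised | Dosed | Post-baseline efficacy assessment |
|---|---|---|---|
| Protocol 9.2 ITT; SAP 4.3.1 | required | – | – |
| Protocol 9.2 mITT | required | required | – |
| SAP 4.2 and 8 ITT | required | required | required |

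The SAP's ITT is narrower than the set that the protocol kept for sensitivity analysis.

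**2. Who is lost.** Two groups: those never dosed, and those dosed who have no efficacy assessment afterwards. SAP 4.2 does not define such an assessment. If one diary day counts, a dosed participant must be lost almost at once to be excluded. If only scheduled visits count, as SAP 5.3 could be read, the first post-baseline CGI-I is at Week 1 (Protocol 8.2.3), and the window is about a week.

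**3. The plan's own figure.** Inputs from SAP 3.1, 3.2 and 4.3.2: "Subjects will be randomized to receive either GNX or PBO in a 1:1 ratio"; "Sixty-four subjects per group provides at least 90% power for the primary endpoint"; a "difference that is at least 25% and a common standard deviation of 43% or less"; and the "Wilcoxon Rank-Sum statistic using a 2-sided significance level of 0.05".

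Power = Φ(Δ/σ × √(n/2) − 1.96) = Φ(25/43 × √32 − 1.96) = Φ(3.289 − 1.960) = Φ(1.329) = 90.8%.

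The t-test version gives 90.4%. A simulated Wilcoxon test on normal data (10,000 trials) gives 89.0%. The stated figure reproduces, so keeping all 128 randomised needs no new sample size. SAP 3.2 counts 128 randomised and dosed while Protocol 9.4 counts about 128 randomised; this is the same ambiguity.

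**4. Responder rate.** The number excluded is an assumption: 1 to 3 of 64 on ganaxolone, none on placebo. The 30.4% rate is the Phase 2 result, borrowed for illustration. Rate among all randomised = rate among those analysed × (64 − k)/64:

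- k = 1: 30.4% × 63/64 = 29.9%, a fall of 0.5 points.
- k = 3: 30.4% × 61/64 = 29.0%, a fall of 1.4 points.

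**5. Primary test.** Losing k per arm costs little nominal power by the formula in step 3: 90.4% at k = 1, 89.9% at k = 2, 88.5% at k = 5.

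To bound the effect of unequal loss, the excluded were put back at the worst possible rank (simulated Wilcoxon, normal data, 25-point effect):

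| Lost, ganaxolone + placebo | Power, excluded | Power, worst rank |
|---|---|---|
| 1 + 0 | 88.5% | 84.6% |
| 2 + 0 | 88.3% | 79.7% |
| 3 + 0 | 88.1% | 73.0% |
| 2 + 2 | 87.8% | 85.9% |

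The worst-rank column is a stress test, not a forecast and not a proposed analysis.

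**6. The count of five.** Setting Protocol 9.3.2.1 beside SAP 4.3.3, four of the protocol's five items have a counterpart in the SAP: missing recording, higher counts after recording stops, maintenance dose achieved, and intercurrent events excluded. The one without a counterpart is mITT.

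**The case against.** **Few people are involved, and sedation is a weak mechanism.** Randomisation and first dose share a visit, so undosed participants should be rare, and failure to take a first dose cannot be caused by the drug. The Day 1 dose is 8% to 10% of target. Protocol 2.2.2.2 says CNS events were dose related, mostly at 500 mg or more, and the schedule above 28 kg reaches 600 mg/day at Day 14. Someone who withdraws for sedation later in titration would normally have diary days and stay in the set. This stands, and it is why the effect is probably small.

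**The mITT run would have shown nothing for the primary endpoint.** The participants it adds have no post-baseline seizure frequency and hence no percent change, so an observed-data Wilcoxon test would be identical in both sets. This also stands. The defect there is an undeclared removal and a wrong count, not the loss of an informative check.

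**The change is disclosed.** Section 8 does show old and new text, and 4.3.1 may simply be unrevised wording. But disclosure does not say which section governs, and the narrower set still departs from the stated estimand.

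**The SAP already has pessimistic rules.** Sensitivity analysis 2 imputes from the highest placebo counts, so a new worst-rank rule is unnecessary. Accepted. As written, though, neither imputation reaches participants whom 4.2 has removed.

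**Conclusion.** The point holds. SAP 4.2 and 8 contradict SAP 4.3.1 and Protocol 9.2, and following 4.2 means analysing a population other than the estimand's, selected on events after randomisation. No efficacy analysis keeps participants who withdraw before dosing or before any post-baseline efficacy assessment. The mITT analysis was dropped without declaration.

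Two stronger readings are tempting and are not supported:

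- *That no analysis keeps early withdrawals.* A dosed participant with a single post-baseline assessment stays in the SAP set, SAP 4.3.3 has caregivers keep recording after drug is stopped, and the Safety Analysis Set holds everyone dosed.
- *That power could really be 73.0%.* That figure needs three exclusions, all on ganaxolone, and a worst-rank penalty that neither document prescribes. Balanced loss of 2 + 2 gives 85.9%.

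The likely size is 0.5 to 1.4 points on the ganaxolone responder rate, resting on an assumed 1 to 3 one-sided exclusions and the Phase 2 rate. The documents give no count. The change is worth making because it aligns analysis and estimand at little cost, not because a large bias is expected.

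**What to change.** 1. In SAP 4.2 and 8, restore ITT as all randomised, to agree with 4.3.1 and Protocol 9.2.
2. For the two key secondary responder endpoints, use all randomised as the denominator and count anyone with no diary data in the period as a non-responder. State this as an exception to the subjects-with-data convention of SAP 4.1. For the maintenance endpoint the rule also covers participants who recorded in titration only; the calculation above does not size that group.
3. For the primary Wilcoxon test, report by arm the number randomised and the number with no post-baseline diary data; SAP 5.5 does not list the number randomised. Apply the imputation rules of sensitivity analyses 1 and 2 to these participants, note the exception to SAP 4.3.8, and add no worst-rank rule.
4. Correct the count in SAP 4.3.3. Either declare the removal of the mITT analysis in section 8 or restore it with the protocol's dosed-only definition. Do not rename the present 4.2 set mITT: the protocol uses that name for a wider set.

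Cost: SAP wording, a denominator rule and an extension of imputation already planned. No change to sample size. The downside is that the ganaxolone responder rate may be marginally lower.
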